This study will enroll an estimated 160 children fulfilling the study eligibility criteria to get 116 evaluable patients over a two year period. The clinical care to these children must be provided by the investigators of this study, namely [name]. In view of the fact that the incidence of cholera vary quite significantly from year to year, it will be important to be very aggressive in the patient enrollment. The investigators have other commitments and responsibilities, and thus they will not be able to remain engaged only with this study. Thus, for providing care to the study children on all seven days of the week, assistance of 50% time of a medical doctor will be required. Because of limited time for completion, it is anticipated that the study may be required to be extended to the Matlab Hospital of the Centre. Although a coinvestigator has not yet been identified, 50% time of a medical officer will also be required to work at Matlab Hospital. The attendants will be required to perform initial screening of the patients, and also to assist in other study works.

The research officer will be responsible to maintain the study drugs and dispense them upon request from the investigators, maintain drug inventory, and store all unused and used drugs. Additionally, the person will be responsible to ensure timely performance of all laboratory test, and to compile and maintain results of all laboratory tests. These will require 100% time of a research officer.

Data will be entered twice as soon as they become available. The person will also help in cleaning of data as well as performing some of the basic statistics, and assist the research officer in performing her tasks. All these activities will require 100% time of a data entry technician.

Ward attendants will be required to screen potential study patients at least at study two locations and possibly also at other hospitals/clinics, and also for motivating parents/legal guardians to bring their children for follow-up visits and to help bringing the patients for follow-up evaluation in the event they fail to return to the hospital in time on their own. For all these activities, it will be essential to recruit two Ward Attendants.

2. Local travel

This will be required for covering the cost for frequent movement of the study medical officer and the investigators to and from Matlab.

3. Supply and material, Other contractual and Interdepartmental

These reflect exact cost of supplies and materials which will be required for the study.

4. Capital cost

This will be required to buy a photocopier which will be extensively used for production of data collection forms, and will remain useful for the office of the investigators.

Other Support

Describe sources, amount, duration, and grant number of all other research funding currently granted to PI or under consideration. (DO NOT EXCEED ONE PAGE FOR EACH INVESTIGATOR)

1. One study, short titled "Short-course ciprofloxacin therapy for childhood shigellosis due to *S. dysenteriae* type I is being conducted. The study is sponsored by Bayer (Pte) Ltd. South Africa through New England Medical Center, Boston, MA. and has a budget of about US \$ 100,000.
2. Another protocol is being developed to determine efficacy and safety of a 7-day course of ciprofloxacin in the treatment of typhoid fever. Anticipated budget for this two-year study will be about 125,000, and it is hoped that the study will be supported by Bayer AG.
3. One research protocol, short titled "Diagnosis of pneumonia in children with dehydrating diarrhoea" is currently being reviewed by USAID under the competitive grant agreement (Tentative budget = US \$ 50,000)
4. Another 3-4 protocols are being developed to test efficacy of antimicrobials in the treatment of shigellosis and cholera, particularly short course therapies. At least two of the protocols are likely to be funded by Pfizer Inc., USA and another by Bayer AG.

Check List

After completing the protocol, please check that the following selected items have been included.

- | | |
|---|-------------------------------------|
| 1. Face Sheet Included |  |
| 2. Approval of the Division Director on Face Sheet |  |
| 3. Certification and Signature of PI on Face Sheet, #9 and #10 |  |
| 4. Table on Contents |  |
| 5. Project Summary |  |
| 6. Literature Cited |  |
| 7. Biography of Investigators |  |
| 8. Ethical Assurance |  |
| 9. Consent Forms |  |
| 10. Detailed Budget |  |

APPENDIX - 2

STUDY FLOW CHART

Activity	Screening	Rehydration	Observation	Day 1	Day 2	Day 3	Day 4	Day 5	F-up
History	+		+	+	+	+	+	+	+
Physical Exam	+		+	+	+	+	+	+	+
Weight	+		+	+	+	+	+	+	+
Vital Signs (4 hourly)	+		+	+	+	+	+	+	+
Intake Output		+	+	+	+	+	+	+	+
Stool Dark-field		+							
Stool Microscopy		+							
CBC + platelet count			+						
Electrolyte, creatinine	+		+	+					
Serum Sp. gr.	+		+	+					
Stool culture for Shigella , Salmonella , and vibrios -			+			+			
Rectal swab culture for vibrios			+	+	+	+	+	+	+
K-B antibiotic susceptibility*				+					
Drug therapy				+	+	+			
Serum drug conc				+	+				
Stool drug conc				+	+				

* will also be determined for *V. cholerae* isolated from cases of microbiological relapse.

ABSTRACT SUMMARY FOR THE ETHICAL REVIEW COMMITTEE

1. The aim of the study is to compare clinical and bacteriologic efficacy of a single dose of azithromycin oral suspension with a 3-day, multiple dose therapy with erythromycin oral suspension in the treatment of clinically severe cholera in children caused by *V. cholerae* O1 or O139 infection. Children who have watery diarrhoea of 24 hours or less, signs of severe dehydration, and have a positive dark field microscopy for *V. cholerae* will be eligible for enrollment. Enrollment of children in the study will require consent of their parents/guardian.
2. The only risk to the patients is the rare possibility of infection consequent to venipunctures to be done for sampling blood on three occasions for determination of serum electrolytes, creatinine and complete blood count (CBC) which will be useful for clinical management of patient, and only once for determination of serum concentration of the study drugs which will not be useful for management of patients.
3. We believe that the very small risk of infection due to venipunctures, and their potential benefit in assessing study children justifies this minor risk.
4. Patient information will be kept under lock, and the computer database on the study children will not include the name of the patients or of the parents/guardians.
5. The parents/guardians will be told of the nature of the study at the time of initial screening by the health worker. The consent form will be given to them to read, or read to them by the investigators for those parents/guardians who are unable to read.
6. A brief one page history form will be filled in by the investigators which will require about 10 minutes of the parent's/guardian's time. The questions do not depart from the questions that would be asked to make a clinical diagnosis under the usual circumstances.
7. The benefits to the patient are that they will be examined by investigators well-trained in pediatrics, and have thorough investigation for their medical problems. The benefits to the general population are that important information may be derived for development of a simple form of antimicrobial treatment for cholera in children which is currently not available. If confirmed, this form of treatment will almost certainly be used in the management of children at the Dhaka Hospital of ICDDR,B.
8. The study will require use of blood, stool and urine samples.

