DESCRIPTION OF THE RESEARCH PROJECT

Hypothesis to be tested:

Concisely list in order, in the space provided, the hypothesis to be tested and the Specific Aims of the proposed study. Provide the scientific basis of the hypothesis, critically examining the observations leading to the formulation of the hypothesis.

The hypothesis of this study is that in the treatment of cholera due to *V. cholerae* O1 or O139 in children aged 1-15 years, a single, 20 mg/kg dose (maximum of 1.0 gram) of azithromycin suspension will be as effective as the conventional, 3-day, multiple dose therapy with erythromycin suspension administered in a dose of 12.5 mg/kg (maximum individual dose of 500 mg) every 6 hours.

Specific Aims:

Describe the specific aims of the proposed study. State the specific parameters, biological functions/ rates/ processes that will be assessed by specific methods (TYPE WITHIN LIMITS).

The specific aims of the protocol are as follows:

1. Primary Aim

The primary aim of this study is to compare the clinical as well as bacteriologic efficacy of a single, 20 mg/kg dose (maximum of 1.0 gram) of azithromycin oral suspension with the conventional 3-day, 12.5 mg/kg (maximum individual dose of 500 mg) 6 hourly dose of erythromycin oral suspension in the treatment of clinically severe cholera in children due to *V. cholerae* O1 or O139.

2. Secondary Aims

The secondary aims of this study are:

- 2.1 To determine the serum and stool concentrations of both study drugs at specified times, and also to determine their serum half-lives.
- 2.2 To determine the minimum inhibitory concentration of *V. cholerae* O1 and O139 to the study drugs.
- 2.3 To monitor and compare the incidence, type and severity of adverse events in association with the study drugs.

Background of the Project including Preliminary Observations

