Because of the high prevalence of multiply-resistant strains of *V. cholerae* and the lack of alternative agents, erythromycin has become the first-line therapy for cholera in children at the ICDDR,B. Erythromycin is administered in multiple doses for 3 days, and it has a high incidence of gastrointestinal adverse events. Because of the problem of resistance, and the lack of a drug safe for use in children that has been demonstrated to be effective when given as single-dose, we propose to study the efficacy of single-dose azithromycin therapy in childhood cholera. Based on a number of attributes of azithromycin, as summarized in the following section, it is reasonable to think that this drug, known to be safe for use in children, would be effective as single dose therapy for cholera in children.

Activity, Pharmacokinetics, and Safety Profile of Azithromycin

The good *in vitro* and *in vivo* activity of erythromycin against intracellular pathogens has been a stimulus for development of the new generation of macrolides. Four new generation macrolides including azithromycin have been synthetically derived from erythromycin through modification of its chemical structure [18,19]. These alterations resulted in better resistance to

the range of pH found in the stomach, and thus better oral bioavailability. They also have better *in-vitro* activity against many pathogens, achieve higher intracellular concentrations, have longer half-lives allowing infrequent dosing, and better tolerability than erythromycin [19-22].

Azithromycin inhibits bacterial protein synthesis by binding to the 50S component of 70S ribosomal subunit. It is 300 times more stable in the range of stomach pH than erythromycin, and has higher oral bioavailability (37% versus 25%). Its absorption, however, is reduced by about 50% in presence of food and antacids [23-25]. After a 500 mg oral dose, a peak serum concentration of 0.4 mg/l is reached in 2-3 hours, and its trough serum concentration 24 hours after a dose is 0.04 mg/l [24,26]. The agent has a low affinity for serum proteins, and protein affinity decreases with increasing serum concentrations of the drug (protein binding of 50% and 12% at drug concentrations of 0.05 mg/l and 0.5 mg/l respectively) [26]. Once the serum peak is reached, concentrations then sharply decline, indicating a rapid distribution phase and a high (23 l/kg) volume of distribution [23,24,26].

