Data on 3,995 patients treated with azithromycin in the United States and Europe in phase II and III trials indicate that its tolerability is comparable to commonly used drugs such as penicillin, amoxicillin and oral cephalosporins, and is markedly better than erythromycin [25,27]. These studies were done on patients with respiratory, sexually transmitted and skin infections, and the total dose used was 1.5 g (500 mg on the first day and 250 mg daily for 4 days). Gastrointestinal disturbances were the most common adverse effects noted; diarrhoea was reported to occur in about 4%, nausea in 3%, and abdominal pain in 3% of the patients. Sixty percent of these adverse events were characterized as mild [25]. This rate of adverse events is much lower than that observed with erythromycin. Severe adverse events were noted in 7% of patients treated with azithromycin compared to 14% of patients treated with other antimicrobial agents, and serious adverse events requiring withdrawal of drug were reported in only 0.7% of the patients taking azithromycin [25]. Interestingly, unlike most antimicrobial agents, adverse events in association with azithromycin were both less common and less serious in children than in adults [25,27]. Azithromycin was not associated with major or consistent effect on laboratory measures of hematological, hepatic or urinary function [25].

Research Design and Methods

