4.2 Secondary outcome variables

- Duration of diarrhoea
- Rates of clinical relapse
- Rates of bacteriologic relapse
- Duration of fecal excretion of *V. cholerae*-O1 or *V. cholerae* O139
- Six-hourly, daily and total volume of watery stool during the study period
- Proportion of patients requiring unscheduled intravenous fluids
- Frequency of vomiting and its volume
- Resolution of diarrhoea among patients in two treatment groups on each study day

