5. HANDLING OF SERIOUS ADVERSE EVENTS

Patients developing serious or life-threatening adverse events will have the study drug stopped, the adverse event appropriately treated, and an adverse event form completed. The investigators must notify the Ethical Review Committee on the event within 24 hours of its occurrence.

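### The ethics summary's statement of risk leaves out the drugs, against the protocol's own text, and the promised adverse-event comparison is missing from the analysis list, with no provision for children who drop out of the evaluable set

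*Protocol*

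**What the plan says.** **Risk statement.** In the Abstract Summary for the Ethical Review Committee, item 2 reads: "The only risk to the patients is the rare possibility of infection consequent to venipunctures to be done for sampling blood on three occasions". The item also mentions one further blood sample for drug concentration. Item 3 judges the study acceptable by setting the small infection risk against the benefit of the blood tests. Neither item mentions the study drugs as a source of risk.

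**Drug risk elsewhere in the protocol.** On the comparator, the Background says: "Erythromycin is administered in multiple doses for 3 days, and it has a high incidence of gastrointestinal adverse events". On azithromycin, the safety profile says: "Severe adverse events were noted in 7% of patients treated with azithromycin compared to 14% of patients treated with other antimicrobial agents". It adds that "serious adverse events requiring withdrawal of drug were reported in only 0.7% of the patients taking azithromycin" and, among gastrointestinal effects, that "diarrhoea was reported to occur in about 4%, nausea in 3%, and abdominal pain in 3% of the patients". Section 5 sets out what happens if a serious or life-threatening event occurs.

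**Promised comparison.** Aim 2.3 is "To monitor and compare the incidence, type and severity of adverse events in association with the study drugs". The project summary names adverse reactions in the two groups as an outcome, and the Ethical Assurance section repeats the comparison as part of the study objective.

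**Listed comparison.** Section 4.2 has "Frequency of vomiting and its volume", and Data Analysis 1.3 has vomiting frequency, amount and daily proportion. Neither list has any other adverse-event item.

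**Who is analysed.** The project summary restricts analysis to children whose culture grows *V. cholerae* O1 or O139 and who remain in hospital at least three days. Section 3.6 expects about 160 enrolled to yield 116 evaluable.

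**The concern.** There are two separate faults.

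First, a summary written for the body that judges risk and benefit makes an exclusive statement about risk that the rest of the document contradicts. An analysis plan cannot repair that.

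Second, tolerability is part of the argument for azithromycin over erythromycin, and three places in the protocol promise to compare it. The analysis list goes into fine detail, down to the amount of vomitus, but omits that comparison. The only analysis population the protocol describes is an efficacy population. If adverse events were compared in it, the children excluded would include any whose early departure was caused by an adverse event. A safety comparison most needs those children, and losing them could make either drug look better tolerated than it was.

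**Working it through.** **1. Risk statement against the protocol body.**

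| Place | Content on drug risk |
|---|---|
| Ethics summary, items 2-3 | None; infection from blood sampling is the sole risk |
| Background | High rate of gastrointestinal events with erythromycin, no figure |
| Azithromycin safety profile | Severe events 7%; withdrawal-level events 0.7%; individual gastrointestinal effects 3-4% |
| Section 3.8 | Procedure for treatment failures |
| Section 5 | Procedure for serious or life-threatening events |
| Project summary; Ethical Assurance | No effective single-dose therapy yet identified in children |

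The first row cannot be reconciled with the others. The last row, with section 3.8, adds possible failure of the test regimen as a risk that the summary omits.

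**2. Children who could be left out of the safety comparison.** The plan's own evaluable number comes first. Section 3.6 gives n = 2 x P x (1 - P) x (Z_alpha + Z_beta)^2 / d^2, with P = 0.95, Z_alpha = 1.645, a type II error of 20% and d = 0.10. This gives 58.74 per arm against 58 stated, so the figure reproduces closely, and 2 x 58 = 116.

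Dosing starts at final enrolment, after a positive dark-field examination. Isolation of the organism is confirmed only after enrolment, so culture-negative children have already been dosed. Hence:

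- dosed but not evaluable: 160 - 116 = 44
- as a share of those dosed: 44 / 160 = 27.5%

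The protocol does not split the 44 between negative cultures and early withdrawals, nor say how many might leave because of an adverse event. The 44 is a planning estimate, since enrolment continues until 116 evaluable children are reached.

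**3. Illustrative event counts.** These apply the azithromycin rates to one arm of 58 (evaluable) or 80 (= 160 / 2, enrolled), assuming the rates carry over.

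| Rate | n = 58 | n = 80 |
|---|---|---|
| Severe, 7% | 0.07 x 58 = 4.1 | 0.07 x 80 = 5.6 |
| Withdrawal-level, 0.7% | 0.007 x 58 = 0.41 | 0.007 x 80 = 0.56 |
| Chance of at least one withdrawal-level event, 1 - 0.993^n | 33% | 43% |

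If the 14% for other antimicrobials is taken as the erythromycin rate, which the protocol does not say, power to separate 7% from 14% at two-sided 5% is 23% with 58 per arm and 30% with 80. The comparison will be imprecise in either population, so there is little reason to give up any dosed child.

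**4. Vomiting.** Vomiting after the first dose mixes cholera with any drug effect. Randomisation balances the cholera component in expectation, so the result is noise rather than bias. Data Analysis 1.1 already compares pre-drug vomiting frequency between groups, so the covariate exists. How much precision adjustment would gain depends on the correlation between pre- and post-dose vomiting, which the protocol does not give.

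**The case against.** A reader might infer that drug risk is neither disclosed nor compared. The protocol does not support that.

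- **Disclosure.** The Ethical Assurance section submits the whole protocol and the consent form to the committee, and requires hazards to be explained to parents. The committee therefore sees the background figures. The consent form is not in the text available, so its content cannot be judged. The contradiction is confined to items 2-3 of the summary.
- **Comparison.** Three statements commit the trial to it. Section 3.5 also compares repeat dosing after vomiting. Section 3.7 directs the daily and follow-up examinations to adverse events, including gastrointestinal distress and rash. The statistical methods give chi-square and Fisher tests for proportions. Section 4 is introduced as a list of effectiveness measures, so the omission there is understandable. Data Analysis 1.3 has no such limit, and that is where the inconsistency lies. Finer safety-table detail may properly sit in an analysis plan that is not shown.

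A reader might also infer that adverse event forms are kept only for serious events, because section 5 says "the adverse event appropriately treated, and an adverse event form completed". That section deals with serious events and requires a form for them. It does not say that other events get none.

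The background rates are weak evidence for this trial. They come from respiratory, sexually transmitted and skin infections treated with 1.5 g over several days. The 14% is not specific to erythromycin, and the protocol says azithromycin events were less frequent and less serious in children. All of this stands, and it limits the counts to illustration. It does not rescue a statement that no risk other than venipuncture infection exists.

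**Conclusion.** The point holds in two limited parts.

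1. Items 2-3 of the ethics summary contradict the Background, the azithromycin safety profile and section 5. This rests on the text alone and needs no assumed rate.
2. Data Analysis 1.3 does not carry through the adverse-event comparison promised in the project summary, aim 2.3 and the Ethical Assurance section. Followed as written, the project summary's restriction could leave about 44 of 160 dosed children (27.5%) out of it. This assumes that the restriction applies to safety as well as efficacy, since the protocol describes no other population, and that planned enrolment is met. How many of the 44 would leave because of an adverse event is unknown.

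The event counts show only that drug risk is not nil on the protocol's own figures; they do not predict this trial. The vomiting adjustment is a matter of precision and secondary. The primary outcomes, sample size and efficacy conclusions are unaffected.

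**What to change.** - **Ethics summary, items 2-3.** Name adverse events of both study drugs, and possible failure of a single dose not yet proven in children, alongside the risk from blood sampling. Make item 3 weigh all of these. If the background rates are quoted, say that they come from other infections and a 1.5 g multi-day regimen, that the 14% is not specific to erythromycin, and that events were less common in children.
- **Data Analysis 1.3.** Add a comparison by group of the number of children with adverse events, the kinds of event and their severity. Base it on all children who received any study drug, whatever their culture result or length of stay. Say in the project summary that the evaluable restriction does not apply to safety. The daily examinations in section 3.7 can supply the data.
- **Vomiting (secondary).** Compare post-dose vomiting with adjustment for the pre-dose frequency already recorded.

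The cost is a few sentences of wording, some recording of severity at examinations already planned, and one baseline covariate. The stated risk becomes less favourable.
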